3.7.5.12 Quality of life measure

The analysis of QOL is deferred to SAP section 3.9.4.

3.7.6 Analysis at 365 \pm 14 Days Following the Initial and Final Infusion

The analysis will be conducted for the ITT population. The analysis template tables for the following efficacy endpoints at 365 \pm 14 days following the initial and final infusion (if applicable) are provided in Appendix 10.

3.7.6.1 The percent reduction in insulin requirement

The insulin requirement will be evaluated at 365 \pm 14 days following the initial and final infusion (if applicable). The reduction percentages from the baseline insulin requirement at both times for a subject, if applicable, are calculated accordingly. The analysis of the reduction percentage adopts the method for a continuous variable.

3.7.6.2 HbA1c

HbA1c is measured at 365 \pm 14 days following the initial and final infusion (if applicable). The analysis of this measure adopts the method for a continuous variable. Change from baseline will also be calculated and analyses will be conducted using the same method.

3.7.6.3 MAGE

The MAGE will be measured at 365 \pm 14 days following the initial and final infusion (if applicable). The first analysis for this variable directly uses MAGE and adopts the method for a continuous variable. Subjects will be categorized into two groups depending on whether the MAGE at 365 \pm 14 days post-transplant is > 11.1 mmol/L or not.

The analysis of the rate of labile diabetes adopts the method for a binary outcome variable.

3.7.6.4 Lability Index

The LI will be measured at 365±14 days following the initial and final infusion (if applicable). The first analysis for this variable directly uses LI and adopts the method for a continuous variable. Subjects will be categorized into two groups depending on whether the $LI \geq 433 \text{ mmol/L}^2/\text{h}\cdot\text{wk}^{-1}$ or not. The analysis of the rate of serious problems with glycemic lability adopts the method for a binary variable.

3.7.6.5 Clarke Score

The Clarke score is given by the investigator according to the Clarke survey questionnaire that gives a total score between 0 and 7 (most severe), where scores of 4 or more indicate reduced awareness of hypoglycemia and increased risk of severe hypoglycemic events. The Clarke score will be evaluated at baseline and at 365±14 days following the initial and final infusion (if applicable). The primary analysis of this variable will treat this variable as continuous and adopts the method for a continuous variable. Change from baseline will also be calculated and analyzed using the same method. For each subject, the indicator of high risk of severe hypoglycemic events will be created according to whether the Clarke score is greater than or equal to 4. The high risk rate of severe hypoglycemic events will be analyzed using the method for a binary outcome variable.

3.7.6.6 HYPO score

The HYPO score will be measured at 365±14 days following the initial and final infusion (if applicable). The analysis of the raw HYPO score adopts the method for a continuous variable. Change from baseline will also be calculated and analyzed using the same method. Subjects with HYPO scores greater than or equal to 1047 will be classified as having severe problems with hypoglycemia, and the analysis of the true rate of this event adopts the method for a binary outcome variable.

3.7.6.7 Basal (fasting) and 90-min glucose and C-peptide (MMTT)

Basal and 90-min glucose and C-peptide derived from MMTT will be measured at 365±14 days following the initial and final infusion (if applicable).

The partial graft function of islet transplantation is indicated by continued C-peptide production. Basal and 90-min glucose and C-peptide derived from MMTT will be measured at 365±14 days following the initial and final infusion (if applicable). The glucose levels (fasting and 90 minute) are a continuous variable and will be analyzed using the method for continuous scale variables. Change from basal to 90 minutes will be calculated and analyzed using the same method. Change from baseline for basal, 90 minutes and the difference between 90 minutes and basal will also be analyzed using the same method.

3.7.6.8 β -score

The β -score will be measured at 365 ± 14 days following the initial and final infusion (if applicable) and is analyzed using the method for a continuous variable. Change from baseline will be calculated and analyzed using the same method.

3.7.6.9 C-peptide/(glucose·creatinine) ratio

This measure accounts for both the dependence of C-peptide secretion on the ambient glucose concentration and the dependence of C-peptide clearance on kidney function [10, 11]. This ratio is a continuous variable and will be measured at 365 ± 14 days following the initial and final infusion (if applicable). The analysis of this variable adopts the method for a continuous variable.

3.7.6.10 Acute insulin response to glucose, insulin sensitivity, and disposition index derived from the insulin-modified frequently-sampled intravenous glucose tolerance test

The insulin modified FSIGT test will be performed at 365 ± 14 days following the initial and final infusion (if applicable). AIR_{glu} , SI and DI, derived from the test, provide a composite measure of β -cell function. AIR_{glu} is calculated as the incremental area-under-the-curve for insulin between 0 and 10 minutes post injection. SI, a measure of insulin-dependent glucose disposal, is derived from Bergman's minimal model using MinMod Millennium software. The DI is calculated by $AIR_{glu} * SI$. The three variables are all continuous and analyzed using the method for a continuous variable.

3.7.6.11 QOL

See the detailed description in SAP section 3.9.4

3.7.6.12 The proportion of subjects receiving a second islet transplant

For each subject, whether the second islet transplant is implemented and will be observable at 365 ± 14 days following the initial and final infusion (if applicable). The true rate of subjects who need a second islet transplant will be analyzed using the method for a binary outcome.

3.7.6.13 The proportion of subjects receiving a third islet transplant

For each subject, whether the third islet transplant is implemented will be observable at 365 ± 14 days following the initial and final infusion. The true rate of subjects who need a third islet transplant will be analyzed using the method for a binary outcome.

3.7.6.14 Proportion of subjects with HbA1c<7.0% and free of severe hypoglycemic events at each center preparing islets

Rates and 95% exact confidence intervals will be reported for each individual center. Rates will be reported at one year and two years after the final transplant. See subgroup analysis (SAP section 3.7.2.1) for the description of a more in depth analysis that may be

used by the individual centers to support licensure of individual islet preparation laboratories.

3.7.7 Analysis at 730±14 Days Following the Initial and Final Infusion

Blood sugar readings are not required more than one year after the final islet transplant. Therefore, we will not be able to compute the Mage, Hypo LI, or β -score at two years. The remaining variables are the same as those observed at one-year after the initial and final transplants and will be analyzed in exactly the same way.

3.7.8 Sensitivity Analysis

The measure of a secondary endpoints may be missing at either 75±5 days or 365±14 days or both, following the initial and final infusion (if applicable). In our analysis report for the secondary endpoints, we will not impute missing values in any of these secondary endpoints. With close monitoring and data validation, the chance of having missing values will be minimized except that some serious adverse events (SAEs) may force subjects to withdraw from the study treatment or withdraw consent without a particular reason during the study. The interpretation of our analysis is strictly applied to the efficacy measurable population. However, a sensitivity analysis will be performed to determine the potential effect that missing values have on the analyses of the secondary endpoints.

- Missing values due to SAE will be excluded from this analysis. The analysis on these subjects will be provided in SAP section 3.8.
- We will conduct a sensitivity analysis assuming a missing at random mechanism: *i.e.*, we assume that a subject will withdraw consent at random with probability r . This probability will be estimated at 75 ± 5 days and 365 ± 14 days following the initial and final infusion (if applicable). The sensitivity analysis will be conducted according to the following two templates (the assumption of missing at random cannot be verified and these results must be viewed with caution.)

For the binary secondary endpoint under consideration, we will fit a logistic regression using the complete baseline data as described in SAP section 3.6. For each missing value, we will draw the outcome randomly from the Bernoulli distribution where the probability is that estimated from the corresponding complete data logistic regression model. The proportion of the secondary endpoint where missing values have been imputed will be compared to that based on the complete data to determine the magnitude of missing values' impact. If the difference between the proportion containing imputed values and that based on complete data is large, then the impact of missing values on the analysis of the endpoint under consideration is large as well; if the difference is small, then the impact of missing values on the analysis is small as well.

We will describe the reliability of this impact using the bootstrap procedure as described below:

- 1) We will resample the complete observations with replacement 1000 times.

- 2) For each bootstrap sample, we will estimate the proportion with missing values imputed in the way described above and calculate the difference between this proportion and that with the complete data.
- 3) We will calculate the standard deviation and construct the 95% bootstrap confidence interval based on the 1000 estimates of the difference.

For a continuous secondary endpoint, we will fit a linear regression using the complete data, given all the baseline information as described in SAP section 3.6. For each missing value, we will impute the outcome by the linear regression using the baseline data. The average of this secondary endpoint with missing value imputed this way will be compared to that based on the complete data to determine the magnitude of missing values' impact.

We will describe the reliability of this magnitude using the bootstrap procedure as described below:

- 1) We will resample the complete observations with replacement 1000 times.
- 2) For each bootstrap sample, we will estimate the average with missing values imputed in the way described above and calculate the difference between this average and that with the complete data.
- 3) We will calculate the standard deviation and construct the 95% bootstrap confidence interval based on the 1000 estimates of the difference.

At both 75 ± 5 and 365 ± 14 days following the initial and final islet transplant (if applicable), we will adopt this sensitive analysis using the methods described above.

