3.7 Efficacy Analyses

3.7.1 Statistical Analysis of Primary Endpoint

HbA1c is the standard measure of glucose control and is used in all major studies as an endpoint for glycemic control. It has been valuable as a risk predictor of diabetes complications. However, since HbA1c is an integrated average, it does not provide information about the range of glucose values a subject experiences. This limitation is a rationale for also including hypoglycemic event occurrence as part of the primary endpoint and various glycemic excursion measures as secondary endpoints.

The primary endpoint for this study is the proportion of subjects with an HbA1c <7.0% at Day 365 AND free of severe hypoglycemic events from Day 28 to Day 365, inclusive, following the first islet transplant, with the day of transplant designated Day 0.

The primary analysis is designed to estimate the true rate of favorable outcomes at one year in subjects in the ITT population pooled over all centers. The proportion of favorable outcomes will be used as the point estimate. An exact one-sided 95% confidence interval will be constructed assuming an underlying binomial distribution for the target population as follows:

If r out of 48 total enrolled subjects achieve the favorable outcome, the exact one-sided 95% confidence interval is given by $p \geq p_L$ where p_L is the solution of the equation

$$0.05 = \sum_{x \geq r} \binom{48}{x} p_L^x (1 - p_L)^{48-x}.$$

0.05 =

The rates of favorable outcome and exact one-sided 95% confidence intervals will be computed for each contributing center.

This analysis will be conducted for the ITT population. The primary endpoint should be available for all treated subjects. An exception will be if a death occurs, if the subject withdraws consent to be followed, or if immunosuppression is begun but the subject never receives a transplant. In these cases the endpoint will be classified as failure to achieve a favorable outcome. Should the endpoint not be evaluated for a particular individual for other reasons, a failure will be imputed unless an evaluation is done at a time longer than one year after transplant, in which case, that later value will be imputed. All imputations will be reported with the primary analysis. The rates and the exact one-sided 95% confidence intervals for complete data and imputed data will be compared to ascertain the sensitivity of the imputation.

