3.7.3 Analysis of Key Secondary Endpoints

Because this is a single intervention study, the tests will be one sided tests for whether

the true rates are greater than the endpoint’s predetermined “minimum rate for efficacy”. These minimum rates were determined by the investigators to be large enough to have credibility for the islet transplant community. The minimum rate for efficacy is provided in Table 7 for each of the key secondary outcomes.

Table 7: Key Secondary Outcomes and Minimum Rates for Efficacy

	Key Secondary Outcome	Minimum* Rate for Efficacy
1	The proportion of subjects with an HbA1c <7.0% AND free of severe hypoglycemic events from Day 28 to Day 730, inclusive, after the first islet transplant.	50%
2	The proportion of subjects with HbA1c ≤ 6.5% at one year after the first islet transplant AND free of severe hypoglycemic events from Day 28 to Day 365 after the first transplant.	50%
3	The proportion of subjects with HbA1c ≤ 6.5% at two years after the first islet transplant AND free of severe hypoglycemic events from Day 28 to Day 730 after the first transplant.	40%
4	The proportion of subjects free of severe hypoglycemic events from Day 28 to Day 365 after the first islet transplant.	50%
5	The proportion of subjects free of severe hypoglycemic events from Day 28 to Day 730 after the first islet transplant.	40%
6	The proportion of subjects with HbA1c <7.0% at one year after the first islet transplant.	50%
7	The proportion of subjects with HbA1c <7.0% at two years after the first islet transplant.	40%
8	The proportion of subjects with HbA1c ≤6.5% at one year after the first islet transplant.	50%
9	The proportion of subjects with HbA1c ≤6.5% at two years after the first islet transplant.	40%
10	The proportion of insulin-independent subjects at one year after the first islet transplant.	20%
11	The proportion of insulin-independent subjects at two years after the first islet transplant.	10%

As with the primary endpoint, the key secondary endpoints should be available for all transplanted subjects and the analysis will be conducted for the ITT population. If an endpoint is not available for a randomized subject then it will be imputed using the same rules that were used for the primary endpoint.

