3.7.4 Additional Efficacy Endpoints

The 11 additional efficacy endpoints are just the key secondary endpoints measured at one and two years following the final islet transplant (the key secondary endpoints are measured at one and two years after the initial transplant). They will be analyzed in exactly the same way as the key secondary endpoints but no adjustment will be made for multiple comparisons.

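### The 3.7.8 sensitivity analysis leaves out SAE-related missing values and fits about 28 baseline terms to fewer than 48 subjects, so it cannot reliably measure the effect of missing secondary endpoints; its no-imputation rule also needs a scope limit.

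*SAP*

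**What the plan says.** **Imputation rules.** SAP 3.7.3 analyses the 11 key secondary endpoints in the ITT population. If an endpoint is not available, "it will be imputed using the same rules that were used for the primary endpoint". Those rules are in 3.7.1. After death, withdrawal of consent, or immunosuppression begun without a transplant, "In these cases the endpoint will be classified as failure to achieve a favorable outcome". For other reasons, "a failure will be imputed unless an evaluation is done at a time longer than one year after transplant", in which case the later value is used. For the 11 final-transplant counterparts, 3.7.4 says "They will be analyzed in exactly the same way as the key secondary endpoints", without a multiplicity adjustment.

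SAP 3.7.8 concerns secondary endpoints missing at day 75 or day 365 after the initial or final infusion and says "we will not impute missing values in any of these secondary endpoints". It limits interpretation to subjects whose efficacy could be measured.

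**Sensitivity analysis.** The same section names SAEs, and withdrawal of consent without a particular reason, as the ways values may go missing. It then says "Missing values due to SAE will be excluded from this analysis" and refers those subjects to 3.8. The remaining values are assumed missing at random. For binary endpoints, "we will fit a logistic regression using the complete baseline data as described in SAP section 3.6"; for continuous endpoints a linear regression is fitted, "given all the baseline information as described in SAP section 3.6". Neither model has variable selection or a penalty. Reliability comes from 1000 bootstrap resamples of the complete observations. For binary endpoints, a small difference between imputed and complete-data results is to be read as a small impact of missing values.

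**The concern.** The purpose of 3.7.8 is to tell the reader whether missing secondary data could change the picture. Two features work against that.

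- The values most likely to be related to outcome, those lost because of an SAE, are set aside before the analysis starts. Section 3.8 contains only safety analyses, so nothing there examines their missing efficacy data.
- The imputation model is close to saturated. An unpenalised logistic model that separates the data has no finite maximum-likelihood fit. Its probabilities go to 0 or 1, and the values drawn for missing subjects then depend on where the fitting routine stops.

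A small reported difference would therefore not show that missingness is harmless. Separately, the no-imputation sentence has no carve-out for the one-year endpoints that 3.7.3 and 3.7.4 impute. An analyst could use either denominator, and the choice can decide a key secondary test.

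**Working it through.** **1. The plan's own figure.** With X ~ Binomial(48, p) and success at 31 or more (SAP 2.4), P(X ≥ 31) is 0.8359 at p = 0.70 and 0.0297 at p = 0.50. Both match Table 3, so the exact binomial tail is the right tool for the tests below.

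**2. Covariate count (SAP 3.6.1 and 3.6.5).**

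| Group | df |
|---|---|
| Age 1, sex 1, race (5 categories) 4 | 6 |
| Diabetes control | 15 |
| Weight, height | 2 |
| QOL measures | 5 |
| Total | 28 |

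The count is 25 if race is one term, and 30 with BMI and two HFS subscales. It is lower if overlapping glucose and C-peptide entries are merged. At 70% success, 48 subjects give 0.30 × 48 = 14.4 failures, or 14.4/28 = 0.51 per term.

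**3. Logistic model.** Covariates were simulated as independent normals unrelated to outcome, with a 70% success rate. Separation was tested by linear programming. Imputation is needed only if someone is missing, so at most 47 subjects are complete. Across repeated runs:

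| Covariates | Data sets completely separated | Bootstrap resamples separated |
|---|---|---|
| 28 | about 99% | 100% |
| 24 | 85-96% | 100% |
| 20 | 50-66% | 98-100% |

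Resamples do worse because they contain fewer distinct subjects.

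**4. Linear model.** A resample of n subjects contains on average n[1 − (1 − 1/n)^n] distinct ones: 30.5 for n = 48 and 28.0 for n = 44. The model has 28 + 1 = 29 parameters, so fewer than 29 distinct subjects makes it rank-deficient. That happens in about 17% of resamples at n = 48 (the limiting case) and 59% at n = 44. The fit to the full set of complete cases exists, but with few residual degrees of freedom: 44 − 29 = 15 at n = 44.

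**5. The two imputation rules on a one-year endpoint with a 50% minimum rate.** The number missing is an assumption, since the SAP gives none. Take 28 observed successes and no later evaluation for the missing subjects.

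| Missing | Not imputed | p | Failures imputed | p |
|---|---|---|---|---|
| 2 | 28/46 | 0.092 | 28/48 | 0.156 |
| 3 | 28/45 | 0.068 | 28/48 | 0.156 |
| 4 | 28/44 | 0.048 | 28/48 | 0.156 |
| 5 | 28/43 | 0.033 | 28/48 | 0.156 |
| 6 | 28/42 | 0.022 | 28/48 | 0.156 |

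The decision rule in 3.7.3 is Benjamini-Hochberg with m = 11 and q* = 0.1, so the cut-off at rank i is 0.1 × i/11. That is 0.0455 at rank 5, 0.0545 at rank 6 and 0.10 at rank 11. A p-value of 0.156 exceeds the largest cut-off and can never be rejected. A p-value of 0.048 is rejected if, for example, at least six of the 11 p-values (itself included) are at or below 0.0545.

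For the 3.7.4 endpoints there is no adjustment. At one-sided 0.05, failure imputation always needs 31/48, while without imputation 30/47, 30/46, 29/45, 28/44, 28/43 or 27/42 is enough for 1 to 6 missing.

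**The case against.** **Scope.** A reader might infer that 3.7.3 and 3.7.8 flatly contradict each other. The documents do not support that. The opening of 3.7.8 uses the time points and phrasing of 3.7.5 and 3.7.6, and no key secondary endpoint is measured at day 75. The key endpoints also have their own specific rule, which would normally govern. This largely stands. What remains is an ambiguity: 3.7.8 states no exemption, and Appendix 10, the day-365 template, lists insulin independence and a 6.5% HbA1c composite alongside the descriptive endpoints.

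**Missing as failure.** It is tempting to say that 3.7.3 counts every missing value as a failure. It does not, because 3.7.1 uses a later evaluation where one exists for the other reasons.

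**The p-value example.** Reading 0.048 against 0.156 as a flip at 0.05 would be wrong for the key endpoints. Under Benjamini-Hochberg a reversal is possible but depends on the other ten tests, and it rests on an assumed number missing.

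**Size of the model.** Several baseline variables overlap, and the β-score is built from others in the list. The 99% figure belongs to the full count; at 20 covariates separation of the observed data is closer to even. The objection does not rescue the bootstrap, which fails at all three counts.

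**Single imputed values.** Giving each missing continuous value its regression prediction, without residual error, looks like a flaw. Because 3.7.8 compares only means and repeats the imputation in each resample, it matters little.

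**Stated caution.** The SAP says that missing at random cannot be verified and that results need caution, and 3.7.2 calls the secondary analyses descriptive. That limits the consequence, but it does not make the small-difference rule sound.

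**Conclusion.** The point holds for supportive analyses. As written, 3.7.8 cannot reliably measure the effect of missing secondary endpoints: it removes a cause of missingness that the SAP expects, and its imputation model is too large for the sample. The failure is clearest for binary endpoints. For continuous endpoints a point fit exists but is unstable, and a sizeable share of resamples cannot be fitted. The separation figures assume independent covariates unrelated to outcome; real associations would make separation more likely, while merging overlapping variables would lower the covariate count.

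The missing carve-out is a smaller, separate fault. It affects the five one-year key endpoints (numbers 2, 4, 6, 8 and 10) and their final-transplant counterparts. It can change a conclusion, as the 28-success example shows, but only under an assumed amount of missing data and, for the key endpoints, depending on the other p-values. The primary analysis has its own rule and is untouched.

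**What to change.** 1. State in 3.7.8 that the 3.7.3 and 3.7.4 endpoints follow the 3.7.3 rule, that is, the primary-endpoint rules of 3.7.1 (failure, or a later evaluation where those rules allow it), and that the no-imputation rule covers only the other secondary endpoints.
2. Include SAE-related missing values in the sensitivity analysis.
3. For binary endpoints, replace the logistic imputation with worst-case, best-case and tipping-point counts over all missing subjects.
4. For continuous endpoints, limit the imputation model to the endpoint's baseline value (where measured) and a small prespecified covariate set. Report how far the SAE-related missing values would have to shift to change the reading.
5. Drop the statement that a small difference means a small impact.

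The exact imputation method in item 4 is partly a matter of preference; the short covariate list and the inclusion of SAE-related values are not. The cost is a few sentences in the SAP and minor programming, with no new data.
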